2.4.6.2 Pharmacodynamics

For all biomarkers noted in the Pharmacodynamics (PD) section of the protocol, the biomarker analyses will be applied to the safety population. The collection for serum immunoglobulin and serum total IgE will be stopped after the approval of protocol amendment 4. The analyses for serum immunoglobulin and serum total IgE in LTS12551 study will be restricted to the patients from DRI12544 study and performed to the data observed up to the end of collection.

For eosinophil count and serum total IgE, IgM, IgA, IgG and IgG subtypes, descriptive statistics (including number, mean, median, standard deviation, Q1, Q3, minimum and maximum), change from baseline and percentage change from baseline over visits will be presented by the treatment category and overall (see Section 2.3.2). In addition, the mean, mean change from baseline, mean percentage change from baseline with corresponding standard error will be plotted across visits by the treatment category and overall (see Section 2.3.2). For biomarkers showing substantial skewness, the geometric means will also be presented.

For eosinophil count, with subgrouping the patients into original baseline EOS ≤ 0.5 Giga/L and >0.5 Giga/L, the mean change from baseline will be plotted over visits for each of the two subgroups and overall. And table showing number (%) of patients who have peak post-baseline EOS count ≥ 1 Giga/L, ≥ 3 Giga/L and ≥ 5 Giga/L will be presented for each of the two subgroups and overall.

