11.4.4.3 Pharmacodynamics

The biomarker analyses will be applied to the safety population. The baseline value for the applicable pharmacodynamic (PD) variables is the original baseline from the parent studies. For all PD parameters, the descriptive statistics (number, mean, median, SD, lower and upper quartiles, minimum and maximum) will be summarized over time for the raw measurements, the change from baseline and percentage change from baseline. Summary plots (mean \pm SEM) over time on the raw measurements, change from baseline and percentage change from the baseline will be presented for the PD parameters.

All parameters will be summarized in descriptive statistics.

11.4.5 Analyses of patient reported outcomes (health-related quality of life / health economics variables)

Change from baseline in the following variables: global measure of AQLQ(S) and the four domains, the quantitative variables of the EQ-5D-3L (single index utility) will be summarized in the same way as described previously for the continuous efficacy variables.

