2.1.3.6.1 Peak expiratory flow

At Visit 1, patients are issued an electronic PEF meter to record morning (AM) and evening (PM) PEF, daily salbutamol/albuterol or levosalbutamol/levalbuterol, morning and evening asthma symptom scores, and number of nighttime awakenings due to asthma symptoms that require reliever medications. Patients are instructed on the use of the device, and written instructions on the use of the electronic PEF meter are provided to the patients. In addition, the investigator instructs the patients on how to record the following variables in the electronic PEF meter:

- AM PEF performed within 15 minutes after arising (between 5:30 AM and 10 AM) prior to taking any salbutamol/albuterol or levosalbutamol/levalbuterol
- PM PEF performed in the evening (between 5:30 PM and 10 PM) prior to taking any salbutamol/albuterol or levosalbutamol/levalbuterol
- Patients should try to withhold salbutamol/albuterol or levosalbutamol/levalbuterol for at least 6 hours prior to measuring their PEF
- Three PEF efforts are performed by the patient; all 3 values will be recorded by the electronic PEF meter, and the highest value will be used for evaluation and it is called PEF maximum (MAX). If more than 3 PEF readings are captured, the highest value of 3 readings closest to the Diary start date and time is the PEF MAX. If only 2 PEF readings are captured, the maximum of the 2 PEF readings captured is the PEF MAX. If only 1 PEF readings is captured, the PEF MAX is treated as missing.

Baseline AM/PM PEF is calculated based on the original baseline values from the parent studies. Baseline AM PEF is the mean AM PEF MAX measurements from the 7 morning diaries

(minimum of 4) prior to randomization in parent study, including the morning diary completed on the randomization day prior to the first dose of IMP. Out of the 7 diaries, if less than 4 have missing PEF value, the baseline AM PEF is the mean of the completed AM PEF MAX within the 7 diaries. If 4 or more diaries have missing AM PEF MAX value, the baseline AM PEF is the mean of the 4 AM PEF MAX prior to and closest to randomization during the whole screening period in parent study.

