2.1.7 Pharmacodynamic/genomics endpoints

2.1.7.1 Whole blood biomarkers

Blood eosinophil count will be measured as part of the standard 5-part white blood cell (WBC) differential cell count on a hematology auto analyzer.

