2.4.6 Analyses of pharmacokinetic and pharmacodynamic variables

The baseline value of PK and PD variables is the original baseline from the parent studies.

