2.5.5 Unscheduled visits

Unscheduled visit measurements of laboratory data, vital signs, and ECG will be included in the by-visit summaries and figures, as well as the computation of baseline, worst values, and PCSAs.

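### The eosinophil subgroup plot sorts patients by the same parent-study baseline count from which it measures change, so regression to the mean lifts the ≤0.5 Giga/L curve and lowers the >0.5 Giga/L curve even if nothing changes

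*SAP*

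**What the plan says.** SAP 2.4.6.2 (Pharmacodynamics) plans an eosinophil figure "with subgrouping the patients into original baseline EOS ≤ 0.5 Giga/L and >0.5 Giga/L". For this figure, "the mean change from baseline will be plotted over visits for each of the two subgroups and overall".

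The reference for change is fixed one level up, in SAP 2.4.6: "The baseline value of PK and PD variables is the original baseline from the parent studies". Protocol 11.4.4.3 agrees: "The baseline value for the applicable pharmacodynamic (PD) variables is the original baseline from the parent studies". The grouping value and the subtracted value are therefore the same number.

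On how that number is obtained, SAP 2.1.7.1 says only that "Blood eosinophil count will be measured as part of the standard 5-part white blood cell (WBC) differential cell count". Averaging is described for diary measures; SAP 2.1.3.6.1, for example, says "Baseline AM PEF is the mean AM PEF MAX measurements from the 7 morning diaries". No such rule is given for eosinophils. SAP 2.5.5 lets unscheduled laboratory samples into the by-visit summaries, "as well as the computation of baseline, worst values, and PCSAs", but does not say that they are averaged.

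A Week 0 pre-dose value is defined in SAP 2.1 and 2.5.4 and shown in the over-time laboratory summaries and plots (SAP 2.4.5.3). In 2.4.6.2 it neither forms the groups nor serves as the reference for change. The section gives no caveat about selection on baseline.

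**The concern.** A reader of a change-from-baseline plot takes zero as the line of no change. That holds in a subgroup only if membership does not depend on the chance error in the baseline value. Here it does. Patients whose baseline was low by chance collect in the ≤0.5 group, and those whose baseline was high by chance collect in the >0.5 group. Later counts drift back in both. LTS12551 has a single arm, so no concurrent control group reveals the drift.

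Biomarkers are a secondary objective, and hypereosinophilia is one of the SAP's selected AE groupings. The figure invites two misreadings. One is a sustained rise on dupilumab in low-eosinophil patients that is not real. The other is a sustained fall in high-eosinophil patients that is not real and that would offset a true rise on this plot.

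**Working it through.** The documents give no expected change, sample size or distribution for this plot, so there is no planned figure to reproduce.

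**1. Direction, without a distribution.** Let X1 be the baseline count, X2 a later count and c = 0.5. Suppose nothing changes, so that X1 and X2 are exchangeable. Patients with both values at or below c contribute zero expected change in total. Hence

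E[(X2 - X1); X1 ≤ c] = E[(X2 - X1); X1 ≤ c, X2 > c].

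This is positive whenever any patient can cross 0.5. The total for X1 > c is its exact negative, and the overall change is 0.

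**2. Size, under assumptions that are mine and not the documents'.** Counts are lognormal with median m. The log-SDs are sb between patients and sw within patient, with no drug effect. Put σ² = sb² + sw², L = ln(0.5/m), M = m·exp(σ²/2) and p = Φ(L/σ), the share at or below 0.5. Then

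D = M·[Φ((L - sb²)/σ) - Φ((L - σ²)/σ)];

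mean change is +D/p in the ≤0.5 group and -D/(1 - p) in the >0.5 group.

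Example with m = 0.25, sb = 0.8, sw = 0.4:
- σ² = 0.64 + 0.16 = 0.80; σ = 0.894; L = 0.693; M = 0.25·exp(0.40) = 0.373; p = Φ(0.775) = 0.781.
- Φ((0.693 - 0.64)/0.894) = Φ(0.059) = 0.524; Φ((0.693 - 0.80)/0.894) = Φ(-0.119) = 0.452.
- D = 0.373 × 0.0712 = 0.0266 (0.0712 is the difference before rounding).
- ≤0.5: 0.0266/0.781 = **+0.034** Giga/L. >0.5: -0.0266/0.219 = **-0.121** Giga/L.

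Over the grid m = 0.20-0.30, sb = 0.6-0.8, sw = 0.3-0.5, the ≤0.5 group shifts by **+0.011 to +0.070** and the >0.5 group by **-0.065 to -0.246** Giga/L.

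**3. Sensitivity (simulation, 1,000,000 patients per scenario).**
- Wider inputs (median 0.20-0.30, total log-SD 0.7-0.9, within-patient correlation 0.5-0.9) give +0.006 to +0.112 and -0.047 to -0.324. At correlation 1.0, meaning no noise, both are 0.
- At median 0.25, log-SD 0.8 and correlation 0.7, a single baseline count gives +0.040/-0.168. An average of two counts gives +0.022/-0.095, and of three +0.016/-0.068. Averaging shrinks the artefact but does not reverse it.
- At the same values, enriching the sample so that half have counts ≥0.3 gives +0.037/-0.167 and moves the overall curve by -0.011.

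**4. Where it comes from.** Grouping on a separate earlier count, with change still taken from baseline, leaves both groups within ±0.001 Giga/L of 0. Keeping the planned groups but taking change from Week 0 leaves both within ±0.002. The double use of one value is the cause.

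**5. Effect of exclusion criterion E 31.** E 31 excludes counts above 1500 cells/mm³ (1.5 Giga/L). If it was applied to the Week 0 sample itself, that value is truncated. Change from Week 0 in the >0.5 group is then +0.01 to +0.11 Giga/L over the step 2 grid (sb at 0.6 and 0.8), while the planned figure shows -0.07 to -0.25 in the same scenarios.

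**6. Illustration.** In the step 2 example, suppose every count truly rises by 20%. The >0.5 group should show about +0.16 Giga/L. The planned plot shows about 0.16 - 0.12 = +0.04.

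**The case against.** A reader might infer that the plan will produce false statistical findings. At the full non-OCS total of 776 + 1902 + 42 = 2720 patients, a 95% interval for mean change would nearly always exclude zero in both subgroups under the assumptions above. The documents do not support that framing. SAP 2.4.6.2 asks for descriptive curves with standard errors. No interval, test or claim is attached, and 2720 assumes that every parent-study patient rolls over, whereas the protocol expects about 2206 in total.

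A reader might also infer that a real eosinophilia signal would be lost. That is too strong. SAP 2.4.6.2 also tabulates peak counts of at least 1, 3 and 5 Giga/L in the same two subgroups. PCSA incidence is reported by status at baseline and at Week 0 (SAP 2.4.5.3). Counts above 3000 cells/µL are reported as AEs (protocol 10.4.5), and hypereosinophilia has its own AE grouping (SAP 2.1.4.1). None of these uses a mean change.

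The SAP also exposes part of the artefact. If the general rules in 2.3.2 and 2.4.5.3 are applied to this figure, the step from baseline to Week 0 in former placebo patients shows the drift before any dupilumab. However, 2.4.6.2 does not say to read it that way.

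Finally, making Week 0 the only reference would be wrong. Protocol 11.4.4.3 fixes the parent baseline. Week 0 is also on drug for about two-thirds of 1902 plus half of 42, that is 1268 + 21 = 1289 of the 2720 at full rollover, and for about half of the 210 EFC13691 patients. For them, change from Week 0 drops anything that began in the parent study. These points stand. They limit the consequence and argue against replacing the figure, but they do not remove the shift.

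**Conclusion.** The concern holds for the two subgroup curves. Their direction under no change follows from the design alone: up in ≤0.5 Giga/L and down in >0.5 Giga/L. The size, about +0.01 to +0.07 and -0.065 to -0.25 Giga/L, rests on assumed lognormal counts. It also takes the baseline to be one count, which is the natural reading but is not stated for eosinophils. The overall curve does not carry this grouping artefact, and the peak-count table uses no change score. The harm is misreading of a descriptive secondary figure. It is not a false test result or an undetected safety signal. A cheap addition is worthwhile; replacing the protocol-defined figure is not warranted.

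**What to change.** Keep the change-from-parent-baseline figure in SAP 2.4.6.2. For the same ≤0.5 and >0.5 Giga/L groups, and separately for Placebo/Dupilumab and Dupilumab/Dupilumab, add:

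- (a) observed mean counts at parent baseline, Week 0 and each visit;
- (b) mean change from the LTS12551 Week 0 pre-dose count, as already defined in SAP 2.1 and 2.5.4.

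State that any comment on a rise or fall on dupilumab within a subgroup rests on the Placebo/Dupilumab curve in (b). Footnote the planned subgroup figure as affected by regression to the mean.

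Cost: one or two extra figures and a few lines of SAP text, with no new data. Two limits belong in footnotes. First, in Dupilumab/Dupilumab patients from EFC13579, EFC13691 and PDY14192, Week 0 is on drug, so (b) omits parent-study changes; this is why (a) is needed. Second, the documents do not say which sample E 31 was applied to. If it was the Week 0 sample, (b) keeps an upward bias of about +0.01 to +0.11 Giga/L in the >0.5 group, under the same assumptions. A small rise there should not be credited to dupilumab.

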2.1.6 Anti-drug antibody (ADA) variables

Samples for anti-drug antibodies (ADAs) are collected at various time points throughout the study. ADA samples collected at Visit 1, Visit 8 (Week 12), Visit 11 (Week 24), Visit 13 (Week 48; if applicable), Visit 15 (Week 72; if applicable), Visit 17 (End-of-Treatment), Visit 18 (End-of-Study) and/or early termination will be analyzed for ADA. The baseline used to define ADA variables refers to the baseline value in the parent study. In response to AE's of special interest like anaphylaxis or hypersensitivity additional ADA samples closer to the event may be analyzed, based on the judgment of the medical investigator and/or medical monitor.

The ADA variables include ADA status (positive or negative) and titer as follows:

• Number of patients with pre-existing immunoreactivity

Pre-existing immunoreactivity is defined as either an ADA positive response in the assay at baseline of the parent study with all post first dose ADA results negative in the current study, or an ADA positive response at baseline of the parent study with all post first dose ADA results in the current study less than 4-fold of the baseline titer levels of the parent study.

• Number of patients with treatment-emergent response in the ADA assay

Treatment-emergent response is defined as a positive response in the ADA assay post first dose in the current study, when baseline status in the parent study is negative or missing. The treatment-emergent response is further characterized as:

- Persistent response defined as a treatment-emergent ADA positive response with two or more consecutive ADA positive sampling time points separated by greater than 12-week period (greater than 84 days), with no ADA negative sample in between.
- Indeterminate response defined as a treatment-emergent response with only the last collected sample positive in the ADA assay.
- Transient response defined as a treatment-emergent ADA positive response that is not considered persistent or indeterminate.
- Number of patients with treatment-boosted response in the ADA assay

Treatment-boosted response is defined as a positive response in the ADA assay post first dose in the current study that is greater than or equal to 4-fold of the baseline titer levels of the parent studies, when baseline status of the parent studies are positive.

- Titer values (titer value category)
 - Low (titer <1,000)
 - Moderate $(1,000 \le \text{titer} \le 10,000)$
 - High (titer >10,000).

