2.4.5 Analyses of safety data

The summary of safety endpoints will be presented by the treatment category and overall (see Section 2.3.2).

General common rules

All safety analyses will be performed on the safety population as defined in Section 2.3.2, unless otherwise specified, using the following common rules:

- The baseline value for safety parameters is defined as the original baseline from the parent studies.
- In addition to the baseline values, the pre-dose measurements at Week 0 in LTS12551 will be presented in the by-visit summary/figure for laboratory, vital signs or ECG parameters. The pre-dose measurements at Week 0 of LTS12551 are defined as follows: for patients enrolled from DRI12544, the measurements at Week 0 are obtained from the EOS visit of DRI12544 if available, regardless whether the EOS visit in DRI12544 was combined with Visit 1/Visit 2 in LTS12551; otherwise, Week 0 value will be the last available measurement prior to the first IMP dose in LTS12551 study. For patients enrolled from the EOT visit of parent studies if available; otherwise, Week 0 value will be the last available measurement prior to the first IMP dose in LTS12551 study. For patients enrolled from the EOT visit of parent studies if available; otherwise, Week 0 value will be the last available measurement prior to the first IMP dose in LTS12551 study.
- The potentially clinically significant abnormality (PCSA) values are defined as abnormal values considered medically important by the sponsor according to predefined criteria/thresholds based on literature review and defined by the sponsor for clinical laboratory tests, vital signs, and ECG (Appendix A).
- PCSA criteria will determine which patients had at least one PCSA during the treatmentemergent adverse event period, taking into account all evaluations performed during the treatment-emergent adverse event period, including non-scheduled or repeated evaluations.

The number of all such patients will be the numerator for the on-treatment PCSA percentage.

- The treatment-emergent PCSA denominator for a given parameter will be based on the number of patients assessed for that given parameter in the treatment-emergent adverse event period by the treatment category and overall (see Section 2.3.2) on the safety population.

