- For quantitative safety parameters based on central laboratory/reading measurements, descriptive statistics will be used to summarize results and change from baseline values by visit and treatment category and overall (see Section 2.3.2). Summaries will include the endpoint value and/or the worst on-treatment value. The endpoint value is commonly defined as the value collected at the date of last IMP dose + 14 days or the end of treatment visit. If this value is missing, this endpoint value will be the closest value prior to the last administration of IMP + 14 days. The worst value is defined as the nadir and /or the peak post-baseline (up to last administration of IMP + 14 days) according to the direction (minimum or maximum) of the abnormality as defined in the PCSA list.
- All of the values including unscheduled measurements will be assigned to the appropriate safety analysis visit window. The safety analysis visit window is defined in Section 2.5.4.
- The analysis of the safety variables will be essentially descriptive and no systematic testing is planned.

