2.4.7.2 Status in the ADA assay in the current study

The following summary will be provided based on ADA population (Section 2.3.5):

- Number (%) of patients with ADA status (negative or positive in the ADA assay) at time points analyzed
 - The summary statistics (including number, median, Q1, Q3, minimum and maximum) of the peak post-baseline titer for ADA positive patients

- ADA titers using descriptive statistics (median, Q1, Q3, minimum and maximum) at ADA time points analyzed
- Number (%) of patients with neutralizing antibody status (negative or positive in the NAb assay) for the ADA positive patients
- Number (%) of patients with pre-existing immunoreactivity
- Number (%) of patients with treatment-boosted anti-drug antibodies.
 - The summary statistics (including number, median, Q1, Q3, minimum and maximum) of the peak post-baseline titer for treatment-boosted ADA patients
- Number (%) of patients with treatment-emergent ADA.
 - The summary statistics (including number, median, Q1, Q3, minimum and maximum) of the peak post-baseline titer for treatment-emergent positive patients
 - Number (%) of patients in the low, moderate or high titer category with treatmentemergent positive response
 - Number (%) of patients with transient, indeterminate, or persistent treatment-emergent ADA response
- Number (%) of patients with neutralizing antibody results (negative or positive in the NAb assay).

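### The peak eosinophil table counts values after the parent-study baseline, so a pre-dose Week 0 value can be reported as a peak on dupilumab

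*SAP*

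**What the plan says.** **Baseline.** SAP 2.4.6 states: "The baseline value of PK and PD variables is the original baseline from the parent studies". SAP 2.4.5 says the same for safety: "The baseline value for safety parameters is defined as the original baseline from the parent studies". SAP 2.1.6 does so for ADA: "The baseline used to define ADA variables refers to the baseline value in the parent study".

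**Eosinophil peak.** SAP 2.4.6.2 plans a "table showing number (%) of patients who have peak post-baseline EOS count" at or above 1, 3 and 5 Giga/L. It is shown overall and split at a parent-study baseline of 0.5 Giga/L. Neither a start nor an end of the counting period is given.

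**Worst value.** SAP 2.4.5 announces: "Summaries will include the endpoint value and/or the worst on-treatment value". It then writes: "The worst value is defined as the nadir and /or the peak post-baseline (up to last administration of IMP + 14 days". An end is given but no start.

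**ADA peak titer.** SAP 2.4.7.2, which covers status in the current study, summarizes the distribution "of the peak post-baseline titer for ADA positive patients".

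**Week 0.** SAP 2.1, 2.4.5 and 2.5.4 define it as a pre-dose time point separate from baseline. For EFC13579, EFC13691 and PDY14192 patients it is the parent end-of-treatment value. For DRI12544 patients it is the parent end-of-study value. If that visit has no value, the last one before the first LTS12551 dose is used.

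**The concern.** In most trials post-baseline and post-first-dose mean the same thing. Here they do not, because baseline lies in the parent study and Week 0 falls between it and the first LTS12551 dose. Taken as written, Week 0 is a post-baseline value and can be the peak.

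This matters most for Placebo/Dupilumab patients, whose Week 0 count precedes any dupilumab. Suppose such a patient has 1.2 Giga/L at Week 0 and stays below 0.6 afterwards. The patient would be tabulated as reaching at least 1 Giga/L in a column that readers take as dupilumab experience. The study has a single arm, so no concurrent control would expose the error. The protocol also gives high eosinophil counts special attention: section 10.4.5 makes on-treatment counts above 3000 cells/µL reportable as AEs.

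For the worst value, one programmer could follow the on-treatment label and another the definition, and they would produce different tables.

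**Working it through.** **1. The plan's own figure and who could be affected.** SAP 1.1 gives parent sizes of 776 (DRI12544), 1902 (EFC13579), 210 (EFC13691) and 42 (PDY14192). Their sum, 776 + 1902 + 210 + 42 = 2930, reproduces the maximum in SAP 1.3. Applying the allocation ratios in SAP 1.1, the expected placebo patients are 776 × 1/5 = 155.2, 1902 × 2/6 = 634, 210 × 1/2 = 105 and 42 × 1/2 = 21. The total is 915.2, or 915.2/2930 = 31%. This is a ceiling that assumes everyone rolls over. The protocol synopsis expects about 2206 patients in all.

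**2. Which rules are anchored to the LTS12551 dose.**
- By-visit tables (SAP 2.5.4, Table 5): the first window after Week 0 opens after the first dose. Anchored.
- PCSA incidence (SAP 2.4.5, 2.4.5.3): limited to the treatment-emergent period. Anchored.
- Treatment-emergent and treatment-boosted ADA (SAP 2.1.6): a result after the first dose in the current study is required. Anchored.
- Worst value (SAP 2.4.5): the label implies treatment, and the treatment epoch in SAP 2.1.4 starts at the first dose, but the definition has no lower bound. SAP 2.5.5 admits unscheduled values without adding one. Ambiguous.
- ADA peak titer (SAP 2.4.7.2): confined to the current study by its heading, but SAP 2.1.6 lists pre-dose Visit 1 among the analyzed samples. Ambiguous for Visit 1 only.
- Eosinophil peak (SAP 2.4.6.2): no start, no end, no label. Not anchored.

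**3. Which rows Week 0 can change.** E 31 excludes counts above 1500 cells/mm³, which is 1.5 Giga/L. If E 31 is applied to the Week 0 sample (the protocol does not name the sample), Week 0 can add entries only to the row for at least 1 Giga/L, because 1.5 is below both 3 and 5.

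**4. Illustrative size.** The documents contain no eosinophil data, so everything here is assumed: log-normal counts, between-patient log-SD 0.7, no drug effect, Week 0 restricted to 1.5 Giga/L or less, and 400,000 simulated patients per scenario. The four on-treatment hematology samples are those of the 48-week flow chart (Weeks 4, 12, 24 and 48). Share with a maximum of at least 1 Giga/L:

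| Median (Giga/L) | Within-patient log-SD | 4 samples | 4 samples + Week 0 | Ratio |
|---|---|---|---|---|
| 0.20 | 0.3 | 3.3% | 3.7% | 1.12 |
| 0.25 | 0.4 | 8.8% | 9.8% | 1.11 |
| 0.30 | 0.5 | 16.8% | 18.6% | 1.11 |

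In the planned subgroup with baseline above 0.5 Giga/L, the middle scenario goes from about 36% to about 40%.

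A simple outer case treats samples as independent, each crossing with probability p. The share then moves from 1 − (1 − p)^4 to 1 − (1 − p)^5. For p = 1% this is 3.9% to 4.9%; for p = 5% it is 18.5% to 22.6%. Samples from one patient are correlated, so the smaller ratio is the more realistic one.

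**The case against.** **The signal is covered elsewhere.** Eosinophil PCSAs are counted only in the treatment-emergent period and shown by status at parent baseline and at Week 0. Hypereosinophilia is a selected AE grouping, and on-treatment counts above 3000 cells/µL are AEs. All of this is right. The table in SAP 2.4.6.2 is one descriptive summary among several, and SAP 2.4.5 says of safety generally: "The analysis of the safety variables will be essentially descriptive and no systematic testing is planned".

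**Week 0 is meant to stand apart.** The SAP presents it in addition to baseline, which suggests three kinds of time point: baseline, Week 0 and post-baseline. That may well be the intention, but no sentence says that Week 0 is not post-baseline.

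**On-treatment already supplies the lower bound for worst values.** This is the natural reading. A conflict between label and definition remains, but it is not an instruction to include pre-dose data.

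**Not every Week 0 high precedes dupilumab.** For Dupilumab/Dupilumab patients from EFC13579, EFC13691 and PDY14192, Week 0 follows uninterrupted treatment. This stands, and it limits misattribution mainly to Placebo/Dupilumab patients.

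**The missing end date is not an error in itself.** The treatment-emergent period deliberately includes follow-up, so ending at the last dose plus 14 days is only one option. This also stands: the SAP needs a stated end, not a particular one.

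**Conclusion.** The point holds as a minor wording defect. The eosinophil peak rule, as written, admits the pre-dose Week 0 value, and the worst-value rule is internally inconsistent. The realistic effect is confined to the row for at least 1 Giga/L, if E 31 governs the Week 0 sample. It is about 1.1-fold under the assumed distributions. That figure rests on no drug effect and on invented medians and variances; the true size cannot be computed from the documents.

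A reader might infer more in three respects:
- **The whole parent-study period enters the peak, including counts on parent placebo.** The most literal reading of the wording allows this. But the SAP says where it takes parent data (baseline, Week 0, medications and the like), and no section brings in intermediate parent laboratory visits. Parent hematology schedules are not in the documents either, so no multiplier for such samples can be supported.
- **The ADA peak titer is equally affected.** Its heading, the ADA population and the response classes all point to the current study. Only the Visit 1 titer needs clarifying.
- **The counts at or above 3 or 5 Giga/L, or the PCSA rates, are inflated.** The PCSA rates are bounded to the treatment-emergent period. The two higher rows cannot be reached by a Week 0 value that satisfies E 31.

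**What to change.** - **SAP 2.4.6.2:** define the peak as the highest count after the first IMP dose in LTS12551, excluding Week 0. State an end date; the treatment-emergent period already used for PCSAs would keep the two eosinophil tables on the same footing.
- **SAP 2.4.5:** add the same start to the worst-value definition so that it agrees with its label. The existing end can stay.
- **SAP 2.4.7.2:** state that the pre-dose Visit 1 titer does not count toward the peak.
- **No change:** keep the parent-study baseline for the 0.5 Giga/L split and for change scores.

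The cost is a phrase in each of three SAP sections and a date filter in the corresponding derivations. No new data are needed.
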